4 EXPERIMENTAL PLAN

4.1 Trial Design

This is a multicenter, OLE trial for patients with RTT who have completed the randomized, double blind, placebo-controlled trial (GWND18064).

Entry to this OLE trial is recommended to be on the same day as Visit 9 of the randomized controlled trial (RCT), GWND18064; however, patients may enter the OLE up to the RCT follow-up visit (Visit 11).

All patients entering this OLE trial will begin dosing with 5 mg/kg/day GWP42003-P (2.5 mg/kg b.i.d.) on Day 1. Patients will be observed, and after 1 week, the dose may further be escalated, at the investigator's discretion, up to 15 mg/kg/day GWP42003-P (7.5 mg/kg b.i.d.) in weekly increments of 5 mg/kg/day (2.5 mg/kg b.i.d.).

Patients should then remain on a stable dose of GWP42003-P for the duration of the maintenance period of the trial (up to 104 weeks), with the option for doses to be decreased or increased to a maximum dose of 20 mg/kg/day (10 mg/kg b.i.d.) based on clinical response and tolerability, as deemed necessary by the investigator, until the optimal dose is found. Patients whose dose has been decreased can have their dose increased again if tolerability improves.

At the end of treatment (Visit 14 [Day 729]), the dose of GWP42003-P will be reduced over a 10-day taper period, and patients will enter the 4-week follow-up period.

If a patient permanently discontinues treatment at any point during the trial, GWP42003-P should be gradually reduced over 10 days (unless inadvisable due to an AE). The patient should attend a withdrawal visit (Visit 14) as soon as possible after the decision is made to permanently discontinue GWP42003-P. If applicable, the patient will taper GWP42003-P, attend the End of Taper visit (Visit 15), and then complete the 4-week follow-up period.

A schematic ([Figure 1-1](#)), presented at the end of [Section 1](#), depicts the overall trial design. More detailed information on treatment and trial procedures is provided in [Section 8](#) and [Section 9](#), respectively.

Study Code: GWND19002
EudraCT Number: 2019-001605-24
Clinical Protocol V2 18Dec19

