4.1.1 Primary Endpoint

Safety:

The long-term safety profile of GWP42003-P will be assessed by evaluating changes in the following, relative to the prerandomization baseline of the RCT:

- AEs
- Clinical laboratory parameters
- Vital signs
- Physical examination procedures
- 12-lead ECG
- Effects on menstruation cycles
- Suicidality
- Change in growth and development by measurement of height, weight, IGF-1 levels, and Tanner Staging (for patients aged ≥ 7 years or earlier, if clinically indicated by the onset of menarche or other signs of precocious puberty)

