12.8 Potential Cases of Drug-induced Liver Injury

All investigational centers are required to submit to GW PVD the laboratory results for any patient after randomization who meets the criteria for the selected laboratory parameters as follows:

- ALT or AST $> 3 \times$ ULN with the appearance of fatigue, nausea, vomiting, right upper quadrant pain or tenderness, fever, rash, and/or eosinophilia ($> 5\%$)
- ALT or AST $> 8 \times$ ULN

Study Code: GWND19002
EudraCT Number: 2019-001605-24
Clinical Protocol V2 18Dec19

- ALT or AST > 5 × ULN for more than 2 weeks
- ALT or AST > 3 × ULN **and** (TBL > 2 × ULN **or** INR > 1.5)

These reports must be sent to GW PVD via e-mail (see [Appendix 2.2](#)) within 24 hours of becoming aware of the results. In addition, a copy of the patient's baseline laboratory results with all reports should be sent to GW PVD.

Abnormal values in AST and/or ALT concurrent with abnormal elevations in TBL that meet the criteria outlined above are considered potential cases of drug-induced liver injury and will be considered as protocol-defined criteria for treatment discontinuation and important medical events. The investigator will arrange for the patient to return to the investigational center as soon as possible (within 24 to 48 hours of notice of abnormal results) for a repeat assessment of ALT, AST, TBL, alkaline phosphatase, gamma-glutamyl transferase levels, eosinophils as well as for testing INR (prothrombin time), detailed history; and physical examination. Patients should be followed this way until all abnormalities have normalized (in the investigator's opinion) or returned to the baseline state. However, if the above transaminase elevation criteria are confirmed by the first set of follow-up laboratory tests, the patient must be withdrawn from the trial.

Elevations in ALT or AST > 3 × ULN **or** TBL > 2 × ULN alone are not considered potential cases of drug-induced liver injury but will be followed as detailed above, within 72 hours' notice of abnormal results. In cases where after Visit 1, ALT or AST are > 3 × ULN, INR testing must be requested. If only the hepatic function monitoring panel was requested and ALT or AST > 3 × ULN, both INR and hematology panel (eosinophils) must be requested. If the patient cannot return to the investigational center, repeat assessments may be done at a local laboratory, and the results should be sent to GW PVD.

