6.1.2 Baseline

For all endpoints, two baselines will be defined:

- the last non-missing observation recorded prior to the first drug administration during GWND18064 lead-in trial will be used as the RCT baseline
- The value reported at Visit 1 during OLE study will be used as the OLE baseline

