9.2 Clinical Laboratory Evaluation

9.2.1 Hematology and Biochemistry

Hematology and biochemistry safety parameters are measured at Visit 1, Visit 4, Visit 5, Visit 6, Visit 8, Visit 9, Visit 10, Visit 12 and Visit 14 (end of treatment).

Summaries will be presented for each laboratory parameter at each visit. Change from baseline (RCT and OLE baseline) and percent change from baseline to each post-baseline visit will also be presented.

If values for any of the parameters are below or above the limit of quantification of the assay (BLQ or ALQ), then they will be included in the summary tables at the BLQ or ALQ thresholds.

Where laboratory samples are repeated, the baseline value is defined as the final recorded value prior to the first dose of IMP during the lead-in trial or prior to Visit 1 in OLE trial.

Shift tables for hematology and biochemistry parameters will be produced, based upon normal ranges and GW toxicity limits (See [Appendix 3](#)), to determine the categorical shifts from each baseline (RCT and OLE) to each post-baseline visit. Values will be categorized as ‘Normal’, ‘Low’ or ‘High’ based on normal ranges and ‘Toxically Low’, ‘Toxically Normal’ or ‘Toxically High’ based on GW toxicity limits.

For eGFR, results will be assigned to the following grades:

- Normal: >60 ml/min/1.73 m²
- Grade 1: 60 ml/min/1.73 m²
- Grade 2: ≥ 30 and <60 ml/min/1.73 m²
- Grade 3: ≥ 15 and <30 ml/min/1.73 m²
- Grade 4: <15 ml/min/1.73 m²

A separate shift table will be produced for eGFR based upon the above grades to determine the categorical shifts from baseline to each post-baseline visit.

An additional table will be produced, summarizing the number of patients meeting the following criteria:

- Alanine aminotransferase (ALT) $> 1 \times \text{ULN}$ at baseline
- Aspartate aminotransferase (AST) $> 1 \times \text{ULN}$ at baseline
- AT $> 1 \times \text{ULN}$ at baseline
- Treatment-emergent ALT $> 3 \times \text{ULN}$, $> 5 \times \text{ULN}$ and $> 8 \times \text{ULN}$
- Treatment-emergent AST $> 3 \times \text{ULN}$, $> 5 \times \text{ULN}$ and $> 8 \times \text{ULN}$
- Treatment-emergent AT $> 3 \times \text{ULN}$, $> 5 \times \text{ULN}$ and $> 8 \times \text{ULN}$
- Treatment-emergent AT $> 3 \times \text{ULN}$ and either bilirubin $> 2 \times \text{ULN}$ or INR > 1.5

where AT is AST or ALT, and treatment emergent is defined as criteria not met at baseline, but

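### Neither SAP baseline is the last value before first GWP42003-P in both prior arms, and the treatment-emergent liver table names neither its baseline nor its window

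*SAP*

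**What the plan says.** SAP 6.1.2 states: "For all endpoints, two baselines will be defined". The first is the lead-in baseline: "the last non-missing observation recorded prior to the first drug administration during GWND18064 lead-in trial will be used as the RCT baseline". The second is the extension baseline: "The value reported at Visit 1 during OLE study will be used as the OLE baseline". Neither depends on what the patient received in the lead-in trial.

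SAP 9.2.1 names both baselines for laboratory changes and for the normal-range and toxicity shift tables. For the table of ALT, AST and either-transaminase elevations it says only that "treatment emergent is defined as criteria not met at baseline, but" met at any time afterwards. SAP 2.2.2 says the safety analyses against the lead-in baseline will be repeated against the extension baseline. That suggests two versions of this table, but 9.2.1 does not say so.

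Protocol V2 Section 4.1.1 frames the primary endpoint this way: "The long-term safety profile of GWP42003-P will be assessed by evaluating changes in the following, relative to the prerandomization baseline of the RCT". On timing, Section 4.1 says: "Entry to this OLE trial is recommended to be on the same day as Visit 9 of the randomized controlled trial (RCT), GWND18064". Section 9.1.1.1 describes the same target as the lead-in end-of-treatment visit.

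**The concern.** The extension is a one-way crossover. Former active patients arrive already exposed, and former placebo patients meet GWP42003-P for the first time. Asking whether an elevation emerged on drug needs a reference taken just before first exposure. That is the lead-in baseline for one group and the extension baseline for the other, and the SAP gives no rule linking baseline to prior arm.

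Long-term safety is the primary objective. Raised transaminases are a named risk in Protocol Sections 3.2.2 and 3.3.3 and have their own withdrawal criteria. The treatment-emergent liver counts are likely to be among the most read results of the trial, so their reference point should be fixed in advance.

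**Working it through.** No sample size, power or error rate underlies this point, so there is no plan figure to reproduce. The check takes each possible pattern and asks whether the SAP definition classifies it correctly.

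**Inputs.** Prior arm (SAP Table 2); transaminase above 3 x ULN at extension entry (yes/no); above 3 x ULN during the extension (yes/no). The criterion is taken as not met at the lead-in baseline. The reference answer is whether the first crossing came on GWP42003-P.

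| Prior arm | At entry | In extension | Onset on drug | Lead-in baseline, extension window | Lead-in baseline, any later time | Extension baseline |
|---|---|---|---|---|---|---|
| Active | no | no | no | no | no | no |
| Active | no | yes | yes | yes | yes | yes |
| Active | yes | no | yes | **no** | yes | **no** |
| Active | yes | yes | yes | yes | yes | **no** |
| Placebo | no | no | no | no | no | no |
| Placebo | no | yes | yes | yes | yes | yes |
| Placebo | yes | no | no | no | **yes** | no |
| Placebo | yes | yes | no | **yes** | **yes** | no |

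Bold cells are wrong. Each of the three readings misclassifies two of the eight patterns. The extension baseline fails only in former active patients. The lead-in baseline with an open window fails only in former placebo patients. With an extension-only window it fails once in each arm.

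**Can the problem patterns occur?** Protocol 6.2.2 excludes patients who met the transaminase discontinuation criteria in the lead-in trial. Section 10 sets those at above 8 x ULN, above 5 x for more than two weeks, or above 3 x with symptoms or eosinophilia, or with raised bilirubin or INR. An isolated, symptom-free 4 x ULN meets none of them. Section 12.8 says such elevations "alone are not considered potential cases of drug-induced liver injury". Entry is therefore possible, subject to investigator judgement under 6.2.1. Values above 8 x ULN, and above 3 x with bilirubin or INR criteria, already bar entry, so only the rows above 3 x and 5 x are exposed to omission. Annex patients enrolling after lead-in Visit 11 are ineligible above 3 x ULN.

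**Illustrative size.** N = 252 is the protocol's planned enrolment. The former active share *s* (1/2 to 2/3) and the rates *p* are assumptions.

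- Left out against the extension baseline = 252 × *s* × *p*(active, elevated at entry and persisting). For *p* = 1%, 5%, 10%: 1.3, 6.3, 12.6 at *s* = 1/2; 1.7, 8.4, 16.8 at *s* = 2/3.
- Wrongly included against the lead-in baseline = 252 × (1 − *s*) × *p*(placebo, elevated at entry and persisting). For *p* = 0.5%, 1%, 2%: 0.6, 1.3, 2.5 at *s* = 1/2; 0.4, 0.8, 1.7 at *s* = 2/3.

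**Does the extension baseline exist?** SAP Table 1, footnote f, requires Visit 1 blood samples only when Visit 1 falls more than 28 days after lead-in Visit 9. Read literally, the 6.1.2 definition gives no laboratory value for a same-day rollover, which is the recommended route. For repeated samples, 9.2.1 takes "the final recorded value prior to the first dose of IMP during the lead-in trial or prior to Visit 1 in OLE trial". That could admit the lead-in Visit 9 result, but it is written for repeats and does not match 6.1.2.

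**The case against.** Much of the needed information is already planned. SAP Table 2 puts former active and former placebo patients in separate columns in all tables. If both versions of the liver table are produced, a careful reader can take the lead-in version for the first group and the extension version for the second. The both-baseline shift tables, the rows for values above 1 x ULN at baseline and the per-patient liver listing would still show someone elevated at rollover, and further progression to a higher threshold would still count. A change from the extension baseline in former active patients is also legitimate: it answers what is new during the extension. The analysis is descriptive throughout.

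These points stand and limit the finding. They leave three gaps. Nothing in the SAP says which version to read for which column. The liver listing also refers to a single unnamed baseline result. The window is undefined: SAP Table 3 lists no lead-in visit other than the baseline, which hints at extension data only, while the liver definition says any time.

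A reader might infer that neither baseline is free of drug for everyone. That is not so: the lead-in baseline precedes the first lead-in dose in every patient, and its weakness is the placebo interval that follows it. A reader might also infer that the shift, vital-sign and ECG tables share the fault. They name both baselines and can stand as planned.

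**Conclusion.** The point holds in a limited form. No single treatment-emergent count in the liver table is right for both prior arms, and 9.2.1 fixes neither the baseline nor the window. Omission is confined to the rows above 3 x and 5 x ULN in former active patients who enter with an isolated elevation. False inclusion is confined to former placebo patients whose elevation arose on placebo. It would go too far to say that signals are lost from the report, because other planned outputs would show these patients.

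The real size is unknown. The documents give neither the allocation ratio nor lead-in transaminase rates, and the SAP Overview says the trial was stopped early, so actual numbers may fall below those based on 252. The missing extension laboratory baseline for same-day rollovers rests on a literal reading of 6.1.2, but it follows directly from the visit schedule.

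**What to change.** In SAP 6.1.2 add a pre-GWP42003-P baseline:

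- patients randomised to GWP42003-P: the lead-in baseline;
- patients randomised to placebo: the last value before the first extension dose, using lead-in Visit 9 when no Visit 1 sample was taken.

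In SAP 9.2.1:

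- use this baseline for the treatment-emergent liver table, shown by prior arm;
- state the window as values after the first extension dose;
- add a row for former active patients whose criterion arose during the lead-in trial and was already met at entry, noting that those who stay elevated appear in both rows.

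With that row all eight patterns above are classified correctly: the former active patient elevated at entry who then resolves appears in the new row, and placebo-period elevations are not counted. Keep the shift and change tables from both planned baselines.

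The cost is one derived baseline and one table row. Prior allocation and lead-in baseline values are already used in the SAP; lead-in Visit 9 results must also be brought in. No new data collection is needed.

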8.2 Concomitant Therapy

It is theoretically possible that GWP42003-P may modify the metabolism of other drugs (including antiepileptic drugs [AEDs]) administered concurrently, and there remains the possibility of pharmacological interactions between GWP42003-P and other concurrently administered drugs. If there are side-effects suspected of being related to an elevation in the concomitant concentration, the investigator should contact the GW medical monitor to discuss best management. Decisions should be based on clinical symptoms and not plasma levels of concomitant medications. The final decision regarding dose adjustments should be taken by the investigator. Cannabidiol has the potential to induce the expression of hepatic CYP enzymes (CYP1A2, 2B6 and 3A4) at clinically relevant concentrations. Careful titration of CBD in patients taking concomitant medications metabolized by CYP3A4, CYP2C19, or CYP2B6 is advised, with plasma monitoring of such medications or their metabolites to be undertaken at the investigator's discretion. Further information on drug interactions can be found in the IB ⁵². Any concerns regarding potential interactions with concomitant medications can be discussed with the trial medical monitor(s).

Changes in concomitant medications are allowed, but increases in dose of medications that affect liver function should be discussed with the medical monitor. Introduction of new medications is allowed, but introduction of new psychotropic and/or central acting agents intended as long-term treatment requires prior discussion with the medical monitor.

The use of rescue medication is allowed, when necessary (i.e., AED for transient exacerbation of seizures). Any medication, other than GWP42003-P, taken during the trial must be recorded on the electronic case report form (eCRF).

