c A safety follow-up Visit 4 weeks after last GWP42003-P dose is required for all patients who withdraw from the trial or complete the trial.

d Informed consent must be obtained prior to any trial-related procedures. In cases where the patient possesses adequate understanding, assent will be taken along with parent(s)/legal representative consent. The nominated caregiver will be asked to complete the quality of life questionnaires.

e Always required.

f Required only if OLE Visit 1 is > 28 days after RCT Visit 9.

g Required if OLE Visit 1 does not occur on the same day as RCT Visit 9.

h Determination of serum IGF-1 levels at Visits 1, 8, 10, and 14 only; IGF-1 laboratory results will remain blinded throughout the trial.

i Hepatic function monitoring is required following increases in GWP42003-P dose or introduction of medications that are known to impact liver function. If the concerned change does not occur within 1 month of a scheduled biochemistry assessment, the investigator should perform an additional hepatic monitoring within 1 month of the change. Hepatic monitoring at Visit 7, 11 and 13 is required for patients taking concomitant valproic acid or whose dose exceeds 15 mg/kg/day.

j The dosing schedule is to be completed by the caregiver daily throughout the trial and reviewed at Visits 2 through 15.

Study Code: GWND19002
EudraCT Number: 2019-001605-24
Clinical Protocol V2 18Dec19

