met at any time post-baseline. The above will be summarized overall and for the following subgroups:

- Valproic acid use (as a concomitant medication) (Yes, No).
- Clobazam use (as a concomitant medication) (Yes, No).
- Valproic acid use and Clobazam use (as concomitant medications) (Yes/Yes, Yes/No, No/Yes, No/No).
(A medication will be considered concomitant if it has a start date on or after the first dose of IMP or if it was started prior to the first dose of IMP and was ongoing.)
- Patients taking 3 or more current AEDs.
- Patients taking 4 or more current AEDs.

All laboratory data will be listed; listings will include limited demographic information about the patient (age, sex, race and weight at baseline). Abnormal laboratory values will be listed separately. A further listing will be created for the laboratory reference ranges and toxicity limits. A listing of liver parameters (ALT, AST, bilirubin and INR) will be produced that includes the baseline result, result at the particular visit, change from baseline, upper limit of normal (ULN) value, ratio of result to baseline and ratio of result to ULN.

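### The valproate and clobazam split of the liver table in SAP 9.2.1 lets drug starts after the ALT/AST rise define the group, and valproate users are scheduled for more liver tests

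*SAP*

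**What the plan says.** SAP 9.2.1 plans a table "summarizing the number of patients meeting the following criteria", with ALT, AST and either-enzyme thresholds at 3, 5 and 8 times the upper limit of normal. Treatment-emergent means not met at baseline but "met at any time post-baseline". The table is given overall and by valproate use, clobazam use and their four-way cross.

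The rule for these subgroups is: "A medication will be considered concomitant if it has a start date on or after the first dose of IMP". A drug started earlier and still ongoing also counts. The rule does not say whether the first dose is the one in the lead-in trial or in the extension. SAP 6.1.8.2 counts from OLE Visit 1, and SAP 9.4.1 treats all medication as concomitant.

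Mid-trial starts can occur. Protocol V2, Section 8.2, says: "Introduction of new medications is allowed", with prior discussion with the medical monitor for new long-term psychotropic or centrally acting drugs.

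On testing, SAP 9.2.1 says hematology and biochemistry are "measured at Visit 1, Visit 4, Visit 5, Visit 6, Visit 8, Visit 9, Visit 10, Visit 12 and Visit 14". Protocol V2, Appendix 1, footnote i, adds: "Hepatic monitoring at Visit 7, 11 and 13 is required for patients taking concomitant valproic acid or whose dose exceeds 15 mg/kg/day". SAP Table 1 repeats that footnote.

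**The concern.** Two separate features affect any reading of 'Yes' against 'No'.

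**Timing.** Group membership can be settled after the outcome. A patient with an isolated ALT rise in month 2 who starts valproate in month 10 is counted as an elevation on valproate. Clobazam is treated the same way.

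**Ascertainment, valproate only.** An 'ever elevated' count rises with the number of tests, and valproate use itself triggers tests. Clobazam does not trigger Visits 7, 11 and 13.

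Safety is the primary objective. Protocol V2, Section 3.2.2, names valproate as the setting in which transaminase elevations were notable, and Section 3.3.3 relies partly on lower valproate use in this population. This is the only summary in the SAP that is split by valproate, so readers will look here for an interaction.

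**Working it through.** The plan states no rate, power or ratio for this table, so there is no figure to reproduce. All event rates below are assumptions.

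**1. Scheduled post-baseline tests (Protocol V2, Appendix 1).**
- All patients: Days 29, 57, 85, 197, 281, 365, 547, 729, which is 8 tests. The largest gap is 547 − 365 = 182 days.
- On valproate throughout, or above 15 mg/kg/day throughout: add Days 141, 456, 638, which is 11 tests. The largest gap is 91 days.
- Up to Visit 10 (Day 365): 6 against 7 tests. A separate end-of-treatment/withdrawal visit with biochemistry makes it 7 against 8.

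**2. Constant, independent risk p per test, no true effect.** P(ever elevated) = 1 − (1 − p)^n.

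| p | n = 11 | n = 8 | Ratio |
|---|---|---|---|
| 0.005 | 0.0536 | 0.0393 | 1.36 |
| 0.01 | 0.1047 | 0.0773 | 1.35 |
| 0.03 | 0.2847 | 0.2163 | 1.32 |

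Stopping around Visit 10, at p = 0.01: 7 against 6 tests gives 0.0679/0.0585 = 1.16, and 8 against 7 gives 0.0773/0.0679 = 1.14. Over p = 0.005 to 0.03 these ratios are 1.16 to 1.15 and 1.14 to 1.13.

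**3. Transient rises, no true effect.** A rise lasting D days is detected if a scheduled test falls within it.
- Onset uniform over 729 days: for D = 14 or 28 the ratio is 11/8 = 1.375; D = 56, 0.731/0.501 = 1.46; D = 84, 0.962/0.693 = 1.39; D = 120, 1.00/0.83 = 1.20.
- Onset exponential with mean 30 to 120 days, D = 28 or 56: from 0.925/0.911 = 1.02 to 0.918/0.718 = 1.28.
- Follow-up ending at Day 365, uniform onset, D = 14 to 120: 1.00 to 1.22.

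**4. Adding late starters.** A simulation of 2,000,000 patients per setting used the SAP rule, the extra panels, full follow-up and no true effect. It assumed 10% or 20% on valproate at Day 1, a further 5% or 10% starting later, a true rise in 15%, and rises of 28 or 56 days with uniform onset or a mean onset of 60 days.
- If a detected rise does not affect later starting, the Yes/No ratio is 1.05 to 1.42, and 7% to 44% of the 'Yes' events come before the drug. The excess over 1 in this case comes from the extra panels.
- If a detected rise prevents later starting, 'Yes' is selected for patients who stayed event-free until they started. The ratio is then 0.56 to 1.27. The low end is 0.0714/0.1274, with 10% at Day 1, 10% late, 28-day rises and mean onset of 60 days.
- Classified by Day 1 use and counted on the eight common visits only, the ratio returns to 0.99 to 1.01.

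**The case against.** Much of the case for leaving the table alone is fair.

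- **Direction.** A reader might infer that both features exaggerate a valproate effect. The documents do not support that. Only the extra panels have a clear direction. Longer follow-up could raise both the chance of starting a drug and the chance of a rise. But Protocol V2, Section 10, withdraws patients with confirmed elevations above 8 times, sustained above 5 times, or above 3 times with symptoms or with bilirubin or INR criteria. That largely closes off later starts for those rows, and patients who do start late must have stayed in the trial. The month-2 example is most plausible for isolated, asymptomatic rises above 3 times the limit.
- **Test counts.** Not every 'No' patient has 8 tests: those above 15 mg/kg/day get the same panels, which dilutes the imbalance. Late valproate starters have fewer than 11.
- **Size.** The extra tests come on Days 141, 456 and 638, while everyone is tested on Days 29, 57 and 85. Early elevations shrink the imbalance. SAP Section 1 says the trial stopped prematurely, but SAP 9.5 says patients complete per protocol, so full follow-up cannot be assumed or ruled out.
- **Which results count.** SAP 9.2.1 omits Visits 7, 11 and 13 from its biochemistry visits, and Table 3 omits Visits 11 and 13. Excluding those results would remove most of the scheduled imbalance, but the any-time wording reads as including them.
- **Status.** The analysis is descriptive, no interaction is tested, and the listings allow case-by-case checks of timing.

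These points limit the size and direction of the bias. They do not remove it: the listings do not correct the summary table, and SAP 9.2.1 carries no caveat about timing or testing frequency.

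**Conclusion.** The point stands as an inexpensive improvement to a descriptive table; no test or error rate is affected. Post-outcome classification applies to valproate and clobazam, and its net direction is unknown. Unequal testing applies to valproate only and favours detection in users. Its size depends on assumptions that the documents cannot settle: a ratio of 1.32 to 1.36 at full follow-up with constant independent per-test risk, about 1.13 to 1.16 with a stop around Visit 10, and 1.02 to 1.28 with early transient rises. All of these set 11 tests against 8, or the truncated equivalent, with no dilution from patients above 15 mg/kg/day. A reader should not conclude that an observed valproate excess must be an artefact, or that the table must overstate the effect. It cannot separate a drug effect from timing and testing, and it could hide a signal as well as create one.

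**What to change.** In SAP 9.2.1:

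1. Define the valproate and clobazam subgroups by use on OLE Day 1, the first OLE dose. This also settles which first dose is meant.
2. Show patients who start either drug later in a separate row, with each elevation marked as before or after the start. Elevations that follow on-trial initiation are then not hidden in 'No'. Classifying by use at the time of the first elevation would not work, because patients without an elevation have no such date.
3. State whether results from Visits 7, 11 and 13 and from unscheduled tests count in the any-time table.
4. Add one companion table restricted to Visits 4, 5, 6, 8, 9, 10, 12 and 14, where all patients have biochemistry.

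The common-visit table equalises scheduled testing. It does not correct for unequal length of follow-up, so the number of patients tested at each visit should be shown beside it.

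The cost is a changed definition, one extra table and a small late-starter row, all from data already collected. Safety monitoring stays as it is.
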